#### **14.9 Exploratory interaction analyses**

Exploratory interaction analyses between the two randomized group for the following baseline and primary efficacy variable:

- FSH total dosage
- Number of normally fertilized oocytes (2PN)
- Number of embryos available for selection

If interaction p-value <0.10 then subgroups analysis will follow.

## 15 SUBSTUDY WITHIN THE CLINICAL INVESTIGATION

**Title of substudy:** Comparing time used for embryo evaluation between the conventional morphology group (control) and iDAScore (treatment) group.

**Background:** One of the potential benefits of using artificial intelligence for embryo selection is time saving given that iDAScore will be at least as reliable in ranking embryos as morphology alone. Therefore, we intend to compare the time used to select an embryo for transfer using the two selection methods in the VISA study (i.e. morphology and iDAScore). The null hypothesis is that there will be no differences between the two methods.

**Materials and methods:** The SD for the difference between the morphological and iDAScore assessment was estimated as 60.6 seconds from a pilot study of 20 patients. To find a mean difference in times between the morphological and iDAScore assessment of 45 seconds with a two-sided Fisher's non-parametric permutation test for paired observations, on significance level 0.05, with a power of 80% then a minimum of 51 patients are needed.

This sub-study will be performed in at least 2 laboratories. To make sure we include cohorts of embryos ranging from few to many, the sites will score embryos of three categories small (2-5 embryos), medium (6-10) and large (>10).

Time for embryo evaluation will measured in the following way:

Once a patient file has been opened in the embryo viewer of the Embryoscope a timer will be started, and embryo scoring performed on all normally fertilized embryos (2PN) using Gardner score. The timer will be stopped once an embryo for transfer has been selected. If the patient is allocated to the treatment group, the timer will be started once a patient file has been opened. Once the iDAScore program has rendered the ranking and an embryo identified with the highest iDAScore the timer will be stopped.

In each of the sites we will analyse the time difference with Fisher's non-parametric permutation test for paired observations and make estimates of the differences between the morphological and iDAScore assessments. The means with 95% CI, SD, median, minimum, and maximum will be calculated.

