5.1.4 Exploratory interaction analyses

Exploratory interaction analyses between the two randomized group and the following baseline variables regarding analyses of primary and selected secondary variables:

- Maternal age
- Number of blastocysts at Gardner Scale 2 or beyond by day 5
- Freeze all

STATISTISKA KONSULTGRUPPEN		Statistical Analysis Plan	
Protocol:		Protocol No: <protocol number>	
eValuating iDA Selection Ability. The VISA study.		Version: 2.0	Page 20 of 25

Model: Outcome = Randomized_Group Baseline_var Randomized_Group *Baseline_var

These analyses should be performed with no other adjustments with Poisson regression model with a robust error variance.

If interaction p-value <0.10 then subgroups analysis will follow regarding primary and selected secondary analyses in subgroups of the baseline variable.

Statistical Analysis Plan (SAP) for the sub study:

Comparing time used for embryo evaluation between the conventional morphology group (control) and iDAScore (treatment) group.

Fisher's non-parametric permutation test for the mean difference between two paired samples will be used to analyze time used for embryo evaluation between the two methods used on the same individuals. For each method mean, SD, Median, minimum and maximum will be given. For the difference between the two methods mean with 95% CI, SD, median, minimum and maximum will be given. Six subjects are the minimum number to be included from each centre.

Separate analyses will also be performed for each site and divided in three categories of number of embryos.

Follow-up for primary efficacy analysis

All patients undergoing a freeze-all cycle for any clinical indication, are expected to return for an embryo transfer within 3 months after their oocyte collection. All freeze-all patients that have not returned for their first rewarmed blastocyst 3 months after the last patient was randomized will be treated as a protocol violations.

STATISTISKA KONSULTGRUPPEN		Statistical Analysis Plan	
Protocol:		Protocol No: <protocol number>	
eValuating iDA Selection Ability. The VISA study.		Version: 2.0	Page 21 of 25

Safety Analyses

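### Timing substudy: the stated inputs need 17 pairs for 80% power, not 51, so number and power do not refer to the same comparison as written

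*Protocol*

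**What the plan says.** Protocol section 15 gives a full set of sample-size inputs in two sentences. The SD of the difference between the two assessments is "estimated as 60.6 seconds from a pilot study of 20 patients". The target is "To find a mean difference in times between the morphological and iDAScore assessment of 45 seconds", using a two-sided paired permutation test. The conclusion is that "on significance level 0.05, with a power of 80% then a minimum of 51 patients are needed".

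The next paragraph of section 15 says "This sub-study will be performed in at least 2 laboratories" and that "the sites will score embryos of three categories small (2-5 embryos), medium (6-10) and large (>10"). The reason given is to cover a range of cohort sizes. Later the section adds "In each of the sites we will analyse the time difference".

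The SAP's substudy text, placed within section 5.1.4, confirms the pairing: it compares "time used for embryo evaluation between the two methods used on the same individuals". It plans separate analyses by site and by the three categories of embryo number. Its only number is "Six subjects are the minimum number to be included from each centre". It gives no total, no number per category and no allowance for dropout.

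**The concern.** The sample-size statement supplies every quantity needed to check it, and the check gives a third of the stated number. A reader who repeats the calculation finds a threefold gap with no explanation in either document. The statement does not say whether 51 was meant to power one overall test or a test within each of several groups.

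What is at stake is limited. If a group-wise basis was meant, the quota that would deliver the power in each group is missing, and 51 patients recruited without quotas need not include 17 in the least common group. If one overall test was meant, the stated power is wrong for the stated number.

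**Working it through.** **Inputs** (all from protocol section 15): SD of the paired difference 60.6 s, mean difference 45 s, two-sided alpha 0.05, power 80%, one pair per patient. The standardised difference is 45/60.6 = 0.743.

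**Attempt to reproduce 51 as one comparison**

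- Normal approximation: n = ((z for 0.975 + z for 0.80) x SD / difference)^2 = ((1.960 + 0.842) x 60.6/45)^2 = 14.2, so 15 pairs.
- Paired t, using the noncentral t with n - 1 degrees of freedom and noncentrality (45/60.6) x sqrt(n):

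| Pairs | Power for 45 s |
|---|---|
| 16 | 79.3% |
| 17 | 82.0% |
| 25 | 94.5% |
| 26 | 95.3% |
| 51 | 99.9% |

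- The planned test itself, by simulation of the paired sign-flip permutation test with all sign patterns enumerated and normal differences: 79.0% at 16 pairs and 82.0% at 17. With moderately skewed differences (gamma, shape 2), 17 pairs give 78% or 94%, depending on the direction of the skew. At 51 pairs, power is at least 99.3% in every case tried.

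The smallest number reaching 80% is therefore 17 for normal differences. For 51 pairs to give 80%, the difference would have to be 24.2 s (SD 60.6 s) or the SD 112.5 s (difference 45 s). Neither figure is in the documents.

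**Other readings of a single comparison**

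| Reading | Number needed |
|---|---|
| One-sided test, 80% power | 13 pairs |
| Two-sided, power 90% / 95% / 99% | 22 / 26 / 36 pairs |
| Bonferroni for 2 / 3 tests | 20 / 22 pairs |
| 60.6 s as the SD of each method, zero correlation | 31 pairs |
| Pilot SD at its 95% limits, 46.1 to 88.5 s (19 df, normality assumed) | 11 to 33 pairs |
| Unpaired two-sample t | 30 per group, 60 in total |

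Inflating 17 to 51 for dropout would need a loss of 1 - 17/51 = two thirds. Splitting 51 over the minimum of two laboratories leaves 25 or 26 pairs in each, with about 95% power. None of these gives 51 patients at 80% power.

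**The one exact match:** 3 x 17 = 51.

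Three cohort-size categories are named directly after the 51, and the SAP plans an analysis in each. Three sites are stated nowhere: the protocol fixes only a lower bound of two laboratories, and the SAP's per-centre minimum is six. The category reading is therefore better supported than a site reading. Under it, 82% is the power within one category. Power in all three at once would be about 0.82^3 = 55%, if the categories are independent and share the same SD and difference.

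**The case against.** The strongest reply is that 51 is right and only a clause is missing. Three categories, an SAP analysis in each and an exact 3 x 17 make it probable that the statistician computed 17 per category and reported the total. On that view the 80% does belong to the calculation behind 51, and an informed reader can work this out. As to intent, this largely stands.

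It does not remove the need for correction. The protocol explains the categories only as a way to cover small to large cohorts; it does not tie the power to a category or set a quota. The SAP's minimum of six per centre does not secure 17 per category either.

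A reader might infer that 51 was miscalculated or that the substudy recruits too many patients. The documents do not support that, because the category reading explains the number exactly.

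A reader might also infer that it is unclear which patients count towards the 51. The documents settle this when read together: the test is paired, the SAP has both methods timed on the same individuals, and protocol section 10.4 restricts iDAScore to the treatment arm. Only treatment-arm patients can supply a pair.

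**Conclusion.** The point holds as a mismatch between a stated number and a stated power. On the protocol's own inputs, 80% power needs 17 pairs, and 51 pairs give about 99.9% for one overall comparison. The likely basis is 17 in each of three cohort-size categories, but that is an inference from the arithmetic and the SAP's planned analyses.

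The 17 assumes approximately normal differences and a true SD of 60.6 s. The 99.9% also assumes independent pairs pooled across laboratories and one common SD across cohort sizes. Uncertainty in the pilot SD moves the requirement to between 11 and 33 pairs, still short of 51.

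The overall timing comparison is not underpowered. The SAP's fixed testing sequence covers clinical pregnancy, live birth and positive hCG, so the substudy is outside the confirmatory testing. Severity is minor.

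**What to change.** Keep 51. The sponsor should confirm its basis and correct the sentence in protocol section 15 so that power and number refer to the same unit.

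- **If the basis is per category**, state: *17 patients with both times measured in each of the three cohort-size categories (51 in total) give 82% power within a category, if the 60.6 s SD and the 45 s difference apply there.* Make 17 per category the recruitment quota.
- **Otherwise**, state that 17 pairs suffice for the single overall test, and that 51 pairs give about 99.9% power, assuming independent pairs pooled across laboratories, one common SD and approximately normal differences.

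The cost is one or two sentences, with no change to the planned total. If the category quota is confirmed, the least common cohort size will set the recruitment time.

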## 7 THE INVESTIGATIONAL DEVICE AND THE COMPARATOR

### 7.1 Identification of the investigational device

|                       |   |
|-----------------------|---|
| Product name          | iDAScore  |
| Software version      | 1.2   |
| Ref nr                | 16536   |
| Basic UDI             | 05712714671005  |
| Manufacturer          | Vitrolife A/S
[name]
SRN: DK-MF-000001892  |
| Description           | 
The iDAScore is a software designed to automatically identify embryos with the highest chance of implantation.
 
During embryo culture in an Embryoscope time-lapse system, images of embryo development are captured on multiple focal planes and time intervals and stored on the ES server. Using information from the ES server, iDAScore assigns a score for each embryo based on a deep learning neural network-based algorithm for predicting viability.
 
The device will not come in contact with tissues or body fluids. It does not incorporate any medicinal products or materials of biological origin.
 
The iDAScore was CE marked under the European Medical Devices Directive 93/42/EEC in early 2020.
 |
| Risk class            | iDAScore is considered a class I accessory for medical devices according to Rule 11 of the Regulation (EU) 2017/745 - Medical Device Regulation.  |
| Intended use          | The device evaluates early embryo development through acquired embryo timelapse videos to assist embryo selection. The device assigns a score to each embryo that identifies embryos with the highest chance of implantation. The device is an adjunct to clinical decision-making, and the final assessment and decision must be made by a medical professional.   |
| Indications for use   | iDAScore is intended to be used for evaluation of embryos from IVF patients. iDAScore must be used together with an EmbryoScope time-lapse system.  |
| Contraindications     | No known contraindications. Contraindications on the patient side regarding a fertility treatment per se are left to the judgement of the physician and are related to the patient. iDAScore does not have any influence on treatment-related contraindications.  |
| Intended target group | There are two different intended target groups. The first group is the patient target group, i.e., patients undergoing fertility treatment. The second group is the user target group, i.e., embryologists, other laboratory personnel and clinic staff at IVF clinics.   |

|   |  |

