### **10.4 Embryology and randomization-blinding-allocation concealment**

Once the oocytes have been retrieved, all embryos will be fertilized by the method of IVF or ICSI as per the individual clinical decision-making and will be incubated in the Embryoscope system until day 5 or 6. As per normal embryoscope protocol, IVF-fertilized embryos will normally be placed in the embryoscope on day 1 and ICSI-fertilized embryos will be placed in the embryoscope on day 0. Exceptions to this can be made due to logistical reasons.

[figure not shown]
All embryos will be incubated using the Embryoscope time-lapse system. Embryo glue will be used as a transfer media in every case.

No analysis of the embryo will be performed by iDAScore until randomization has occurred and no other time lapse algorithms will be applied to the embryos of patients who have been recruited to this study. After randomization, iDAScore will only be applied to the treatment group.

On day 5 an embryologist will score all embryos according to the Gardner scale by visual selection using the Embryoscope software and make a preliminary decision on which embryo is prioritized for embryo transfer. If two or more early blastocysts are available (i.e. at the developmental stage of 2 or more according to the Gardner scale) between 114 and 118 hours post insemination (hpi), the patient is randomized using a 1:1 ratio. If there are fewer than two early blastocysts, randomization will not take place, and this will be recorded in the eCRF.

If randomized to the control group, the preliminary decision on embryo prioritization for transfer remains unchanged. If, however, the patient is randomized into the treatment group, the sequences of all normally fertilized embryos will be analyzed using the iDAScore software and the embryo with the highest score is prioritized for transfer.

Randomization will be performed with the use of a randomization module within the eCFR program. If, for some reason, randomization from within the eCRF is not possible, manual randomization will be performed by flipping a coin and the randomization outcome shall be registered once the database is accessible.

*Patients will be randomly allocated to two different study groups:*

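### The time substudy stops its two clocks at different events, so any human check made after the iDAScore ranking is left out of the iDAScore time only

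*Protocol*

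**What the plan says.** Protocol section 15 sets out to compare the time needed to choose an embryo by the two methods. Both clocks start when the patient file is opened. They stop under different rules:

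- Morphology: "The timer will be stopped once an embryo for transfer has been selected".
- iDAScore: "Once the iDAScore program has rendered the ranking and an embryo identified with the highest iDAScore the timer will be stopped".

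Section 7.1 describes the device as an adjunct and adds that "the final assessment and decision must be made by a medical professional". The table in section 11.2 foresees that the highest-scoring embryo may be overruled; morphology then determines the choice and the subject is marked as withdrawn. Sections 10.4 and 15 do not say where in the timing that review falls.

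On order, Protocol section 10.4 has all embryos graded and a preliminary choice made before the patient is randomised. It also states: "No analysis of the embryo will be performed by iDAScore until randomization has occurred". Afterwards iDAScore is run in the treatment group only.

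On analysis, section 15 names a "two-sided Fisher's non-parametric permutation test for paired observations". The SAP's substudy text (at the end of section 5.1.4) confirms the pairing: it compares "time used for embryo evaluation between the two methods used on the same individuals".

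**The concern.** A comparison of durations needs the same start and the same finish. Here the finish differs. The morphology time includes the human act of choosing. The iDAScore time ends when the top-scoring embryo has been identified, before any final assessment or review of that embryo. Whatever that later step takes is absent from one side of the difference only, and it enters the result as time saved. More patients would not remove this; they would only estimate the same shifted difference more precisely.

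The second feature is order. A pair needs both methods on one patient. iDAScore is run only in the treatment group and only after grading and randomisation, so every pair is morphology first and iDAScore second. Neither document describes a reversed order, a second reader, a gap between timings or an adjustment for order. If order matters, its effect is fully confounded with method.

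At stake is the substudy's conclusion on time saving. The main trial's endpoints are not involved.

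**Working it through.** **Inputs from the documents (Protocol section 15).** "The SD for the difference between the morphological and iDAScore assessment was estimated as 60.6 seconds from a pilot study of 20 patients". The target is stated as: "To find a mean difference in times between the morphological and iDAScore assessment of 45 seconds". Two-sided level 0.05, power 80%, minimum 51 patients.

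**The plan's figure of 51.**

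- Normal approximation for one paired comparison: n = (60.6 × (1.960 + 0.842) / 45)² = 14.2, so 15.
- With the t distribution: 17 (power 79.3% at n = 16 and 82.0% at n = 17). A simulated sign-flip permutation test gives 78.5% and 81.1%.
- Section 15 uses three cohort-size categories, and 17 × 3 = 51. This matches the stated number exactly. The protocol does not state the multiplication, so the explanation is an inference.

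The sample size is therefore not in dispute. With 51 pairs analysed together, power is 99.9% for 45 s and 80% for a difference of about 24 s.

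**How small a shift would matter.** The standard error of the mean difference is 60.6 / √51 = 8.49 s. The two-sided 5% critical value on 50 degrees of freedom is about 2.009, so an observed mean of 2.009 × 8.49 ≈ 17 s is already significant.

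**Illustration.** Let b be the seconds of human assessment left out of the iDAScore time. The documents give no value for b, so a range is assumed. If the true difference is zero, the test statistic has noncentrality b / 8.49, and the chance of a significant result in favour of iDAScore is:

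| b (assumed) | n = 51, pooled | n = 17, one category |
|---|---|---|
| 0 s | 2.5% | 2.5% |
| 5 s | 8% | 5% |
| 10 s | 21% | 9% |
| 15 s | 41% | 16% |
| 30 s | 93% | 48% |

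For n = 17 the standard error is 60.6 / √17 = 14.7 s. These figures are the test's rejection probabilities at assumed shifts. They show how sensitive the result is and do not show that a shift of any given size exists.

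**Stop points side by side.**

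| Step | Morphology clock | iDAScore clock |
|---|---|---|
| File opened | included | included |
| Embryos graded, or ranking produced | included | included |
| Top embryo identified | included | included |
| Human choice of the embryo for transfer | included | not included as worded |
| Review that may overrule the top score | not applicable | not included as worded |

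**The case against.** The best reply is that the gap is small. Under Protocol section 10.4, in both its general text and its treatment-group description, the highest score determines which embryo is prioritised, so identifying it is close to selecting it. The morphology choice at that stage is itself called preliminary, so both clocks could be read as stopping at prioritisation. Section 11.2 treats an overrule as an exception and describes no routine check of every top-ranked embryo. The requirement in section 7.1 is an intended-use statement with no duration attached. All of this stands, and it narrows the gap. It does not close it: the intended use calls for a human decision with the device, an overrule presupposes that someone looks at the embryo, and neither is timed.

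A reader might go further and infer that familiarity with a cohort just graded always favours iDAScore and is counted as time saved. The documents do not support that. As worded, the iDAScore clock contains no grading for familiarity to speed up, and neither document says that the same embryologist performs both timings. The fixed order is established; a carry-over effect is not.

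A reader might also take the 41% or 93% above as evidence of bias, or conclude that a significant result would be worthless. Neither follows, because b is unknown. Analyses by site or by cohort-size category, with fewer pairs, would also be less sensitive to a given shift.

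**Conclusion.** The concern holds as a measurement asymmetry. By the wording of section 15, the two clocks stop at different events, and any time spent on the final human assessment or on review of the top-ranked embryo falls outside the iDAScore time alone. The size of this cannot be obtained from the documents, and the default-choice rule may keep it small. With 51 pairs, an omitted step of 10 to 15 s would be enough to raise the chance of a spurious significant saving from 2.5% to between about 21% and 41%, given SD 60.6 s and no true difference.

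The order of the two timings is fixed in every pair, so an order effect cannot be separated from the method. Its size and direction are not shown.

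Severity is minor. The substudy feeds no primary or secondary endpoint and lies outside the fixed-sequence testing in the SAP.

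**What to change.** In Protocol section 15 and the SAP's substudy text:

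1. Use one stop event for both clocks: the embryologist's recorded confirmation of the embryo for transfer, including any review of the top-ranked embryo and any overrule. Because section 11.2 marks overruled subjects as withdrawn, say how their timings are handled.
2. State that pairs come only from treatment-arm patients, with morphology first and iDAScore second, and who performs each timing. The substudy's title reads as a comparison between randomised groups and should be reconciled with the paired analysis.
3. Word the conclusion as time for iDAScore selection after morphological grading.

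The cost is a wording change and one more recorded time point, probably with a smaller apparent saving. Repeating both timings on stored sequences in random order could address the order effect, but it is optional extra work, and familiarity would remain unless the reader had not seen the cohort before.
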